6.3 INTERIM ANALYSIS

Interim analyses of efficacy, safety, and other data will be performed after 14 patients are treated at each dose level at the end of the Part 1. Further statistical details are provided in [Section 11.5](#).

A preliminary statistical evaluation of antitumor activity by RECIST 1.1 will be done on the first 14 patients treated in each cohort; if at least 2 confirmed responses (PR or CR) in at least 1 cohort are observed then the study can continue in Part 2, if the safety profile is acceptable.

In addition to the efficacy criteria, safety criteria including the number (%) of patients experiencing an eye disorder leading to dose modification or drug discontinuation, or peripheral neuropathy, or a treatment-emergent adverse event (TEAE) leading to dose reduction or drug discontinuation, will be considered.

In case of the efficacy criteria (<2 PR or CR in 14 patients) not being reached for a given dose, then this dose will not be selected.

In case of neither dose reaching the efficacy criteria (<2 PR or CR in 14 patients), then the study will be stopped.

In case of comparable ORR and safety profiles between 90 mg/m² D1D8 q3w and 120 mg/m² D1D8 q3w, then the lower dose (90 mg/m² D1D8 q3w) will be chosen.

In case of a higher ORR in 120 mg/m² D1D8 q3w and a comparable safety profile to 90 mg/m² D1D8 q3w, then 120 mg/m² D1D8 q3w will be chosen.

In case of a higher ORR in 120 mg/m² D1D8 q3w and a better safety profile with 90 mg/m² D1D8 q3w, then the dose will be selected on the best risk/benefit.

If there are 6 responses or more in the first 14 patients treated at 1 dose, then the study could be stopped for overwhelming efficacy.

6.4 STUDY COMMITTEES

A Steering Committee including the Study Chairman, 2 main Investigators, Sponsor representatives and an ad hoc ophthalmologist expert, as needed, will be responsible for:

- Supervising the progress of the trial towards its overall objectives,
- Reviewing at regular intervals relevant information that may affect the study conduct, and,
- Reviewing the safety and efficacy including the interim analysis for ORR.

7 SELECTION OF PATIENTS

7.1 INCLUSION CRITERIA

- I 01. Metastatic TNBC
- I 02. Patient with measurable disease, as per RECIST 1.1 criteria ([Appendix A](#)).
- I 03. Histologically documented TNBC (either at primary diagnostic or at metastatic site) that is ER-negative and PgR-negative (<1% tumor staining by IHC), and HER2 nonoverexpressing by IHC (0, 1+) or in situ hybridization-negative based on single-probe average HER2 copy number <4.0 signals/cell or dual-probe HER2/CEP17 ratio <2 with an average HER2 copy number <4.0 signals/cell as per ASCO guidelines (2).
- I 04. Patients with CA6-positive disease defined as membrane intensity of 2+, 3+ in $\geq 30\%$ of tumor cells (**Part 1 and Part 2a**) or with at least 1% positive tumor cells at intensity $\geq 1+$ and <30% of tumor cells at intensity of 2+, 3+ (**Part 2b**).
- I 05. Patients received at least 1 prior chemotherapy regimen but no more than 3 for advanced/metastatic disease:
- a) Adjuvant/neo-adjuvant chemotherapy will be counted as a prior chemotherapy for metastatic/recurrent disease if the patient had a progression/recurrence within 6 months after completion of the treatment,
 - b) Prior hormonal, biologic (eg, bevacizumab) or immunotherapy, without a cytotoxic agent, are allowed and are not counted as a line of therapy,
 - c) A chemotherapy line in advanced/metastatic disease is an anticancer regimen that contains at least 1 cytotoxic chemotherapy agent and was discontinued due to progression. If a cytotoxic chemotherapy regimen was discontinued for a reason other than disease progression then this regimen does not count as a “prior line of chemotherapy” unless this regimen was discontinued after treatment response (CR, PR or SD) and disease progression occurred before another line of chemotherapy.
- I 06. Prior anticancer therapy must have contained anthracycline (eg, doxorubicin), if not contraindicated, and a taxane (eg, docetaxel, paclitaxel) in an adjuvant/neo-adjuvant or metastatic setting.
- I 07. Signed written informed consent.

7.2 EXCLUSION CRITERIA

Patients who have met all the above inclusion criteria listed in [Section 7.1](#) will be screened for the following exclusion criteria which are sorted and numbered in the following 2 subsections:

7.2.1 Exclusion criteria related to study methodology

- E 01. ECOG performance status ≥ 2 ([Appendix B](#)).
- E 02. Patient less than 18 years old.
- E 03. Any severe acute or chronic medical condition including uncontrolled diabetes mellitus, history of cardiovascular disease (congestive heart failure, severe or unstable angina pectoris, recent myocardial infarction within last 6 months, history of clinically significant active chronic obstructive pulmonary disease [COPD], or other moderate-to-severe chronic respiratory illnesses present within last 6 months), which in the Investigator's opinion, may impair the ability of the patient to participate in the study, or interfere with interpretation of study results, or make the patient unable to comply with the study procedures.
- E 04. Pregnant or breast-feeding women.
- E 05. Patients with reproductive potential who do not agree to use accepted and effective method of contraception during the study treatment period and for 6 months following discontinuation of study drug. The definition of "effective method of contraception" described hereafter: oral contraceptives, combined hormonal intravaginal, transdermal, intrauterine device or condoms will be based on country-specific regulatory requirements, and documented in the Informed Consent Form ([Appendix C](#)).
- E 06. Adverse events (excluding alopecia and those listed in the specific exclusion criteria) from any prior anticancer therapy of Grade >1 (National Cancer Institute Common Terminology Criteria for Adverse Events [NCI CTCAE] v4.03; see [Appendix D](#)) at the time of randomization.
- E 07. Wash out period of less than 3 weeks or 5 half-lives from previous antitumor chemotherapy, immunotherapy or any investigational treatment.
- E 08. Patient has received wide field radiotherapy ≤ 4 weeks prior to starting study treatment, or limited field radiation for palliation ≤ 2 weeks prior to starting study treatment, or has not recovered from the side effects of such therapy.
- E 09. Patient has undergone major surgery ≤ 3 weeks prior to starting study treatment or has not recovered from the side effects of major surgery.
- E 10. History of brain metastasis (other than totally resected or previously irradiated and nonprogressive/relapsed), spinal cord compression, or carcinomatous meningitis, or new evidence of brain leptomeningeal disease.
- E 11. Prior malignancy. Adequately treated basal cell or squamous cell skin or superficial (pTis, pTa, and pT1) and bladder cancer are allowed, as well as any other cancer for which treatment has been completed ≥ 3 years ago and from which the patient has been disease-free for ≥ 3 years.

- E 12. Participation in another clinical trial and any concurrent treatment with any investigational drug within 30 days prior to randomization.
- E 13. Prior treatment with eribulin as last therapy prior to enrollment, or prior maytansinoid treatments (DM1 or DM4 ADCs).

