15 CLINICAL TRIAL PROTOCOL AMENDMENTS

All appendices attached hereto and referred to herein are made part of this clinical trial protocol.

The Investigator should not implement any deviation from, or changes to the clinical trial protocol without agreement by the Sponsor and prior review and documented approval/favorable opinion from the IRB/IEC and/or notification/approval of health authorities (competent regulatory authority) of an amendment, as required by local regulation, except where necessary to eliminate an immediate hazard(s) to clinical trial patients, or when the change(s) involves only logistical or administrative aspects of the trial. Any change agreed upon will be recorded in writing, the written amendment will be signed by the Investigator and by the Sponsor and the signed amendment will be filed with this clinical trial protocol.

Any amendment to the clinical trial protocol requires written approval/favorable opinion by the IRB/IEC prior to its implementation, unless there are overriding safety reasons.

In case of substantial amendment to the clinical trial protocol, approval from the health authorities (competent regulatory authority) will be sought before implementation.

In some instances, an amendment may require a change to the informed consent form. The Investigator must receive an IRB/IEC approval/favorable opinion concerning the revised informed consent form prior to implementation of the change and patient signature should be re-collected if necessary.

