Appendix C Guidance on contraceptive methods and collection of pregnancy information

DEFINITIONS

Nonreproductive potential

1. Premenopausal female with 1 of the following:
 - Documented hysterectomy,
 - Documented bilateral salpingectomy,
 - Documented bilateral oophorectomy.
2. Postmenopausal
 - A postmenopausal state is defined as no menses for 12 months without an alternative medical cause. A high follicle stimulating hormone (FSH) level in the postmenopausal range may be used to confirm a postmenopausal state in women not using hormonal contraception or hormonal replacement therapy (HRT). However, in the absence of 12 months of amenorrhea, a single FSH measurement is insufficient.
 - Females on hormone replacement therapy (HRT) and whose menopausal status is in doubt will be required to use 1 of the highly effective contraception methods if they wish to continue their HRT during the study. Otherwise, they must discontinue HRT to allow confirmation of postmenopausal status before study enrolment.

Reproductive potential (WOCBP)

A woman is considered of reproductive potential (WOCBP), ie, fertile, following menarche and until becoming postmenopausal unless permanently sterile. Permanent sterilization methods include hysterectomy, bilateral salpingectomy and bilateral oophorectomy.

CONTRACEPTIVE GUIDANCE

Male subjects

- Male subjects with heterosexual partners of reproductive potential (WOCBP) are eligible to participate if they agree to use the following during the protocol defined timeline:
 - Refrain from donating sperm,

and

 - At least 1 of the following conditions applies:
 - Are and agree to remain abstinent from penile-vaginal intercourse on a long term and persistent basis, when this is their preferred and usual lifestyle.

or

 - Agree to use a male condom plus an additional contraceptive method with a failure rate of <1% per year (see table for female subjects).
- Men with a pregnant or breastfeeding partner must agree to remain abstinent from penile-vaginal intercourse or use a male condom for the time defined in the protocol

Highly Effective Contraceptive Methods That Are User Dependent Failure rate of <1% per year when used consistently and correctly^a

• Combined (estrogen- and progestogen-containing) hormonal contraception associated with inhibition of ovulation^b
– Oral,– Intravaginal,– Transdermal.

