
• Progestogen-only hormone contraception associated with inhibition of ovulation^b
– Oral,– Injectable.
Highly Effective Methods That Are User Independent

• Implantable progestogen-only hormone contraception associated with inhibition of ovulation^b.

• Intrauterine device (IUD).

• Intrauterine hormone-releasing system (IUS).

• Bilateral tubal occlusion.

• Vasectomized partner. (Vasectomized partner is a highly effective contraceptive method provided that the partner is the sole sexual partner of the woman of childbearing potential and the absence of sperm has been confirmed. If not, an additional highly effective method(s) of contraception should be used. Spermatogenesis cycle is approximately 90 days.)

• Sexual abstinence. (Sexual abstinence is considered a highly effective method only if defined as refraining from heterosexual intercourse during the entire period of risk associated with the study drug. The reliability of sexual abstinence needs to be evaluated in relation to the duration of the study and the preferred and usual lifestyle of the subject.)
NOTES: 
a) Typical use failure rates may differ from those when used consistently and correctly. Use should be consistent with local regulations regarding the use of contraceptive methods for subjects participating in clinical studies.
 
b) Hormonal contraception may be susceptible to interaction with the study drug, which may reduce the efficacy of the contraceptive method. In this case TWO highly effective methods of contraception should be used during the treatment period and for at least 6 months [corresponding to time needed to eliminate study treatment plus 30 days for study treatments with genotoxic potential] after the last dose of study treatment.

Female subjects:

Highly Effective Contraceptive Methods That Are User Dependent
Failure rate of <1% per year when used consistently and correctly^a

• Combined (estrogen- and progestogen-containing) hormonal contraception associated with inhibition of ovulation^b
– Oral,– Intravaginal,– Transdermal.

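### Exclusion criterion E05 accepts condoms as a sole method, while Appendix C makes a man with a partner of reproductive potential ineligible on a condom alone, and E05 does not say which text controls

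*Protocol*

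**What the plan says.** E05 appears with the same wording in the protocol synopsis and in Section 7.2.1. It excludes patients of reproductive potential who will not use an effective method during treatment and for 6 months afterwards. It then lists five methods joined by a single final or: oral contraceptives, combined hormonal intravaginal, "transdermal, intrauterine device or condoms will be based on country-specific regulatory requirements". No second method is asked for. The same sentence says that the definition is documented in the consent form and gives Appendix C in brackets.

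Appendix C sets out the detail:

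- **Men whose partners are of reproductive potential.** Male subjects with "partners of reproductive potential (WOCBP) are eligible to participate if they agree to use the following". The first condition is "Refrain from donating sperm". It is joined to a choice of abstinence or "Agree to use a male condom plus an additional contraceptive method with a failure rate of <1% per year".
- **Men whose partner is pregnant or breastfeeding.** "Men with a pregnant or breastfeeding partner must agree to remain abstinent from penile-vaginal intercourse or use a male condom". Here a condom alone is accepted.
- **Women on HRT whose menopausal status is in doubt.** They "will be required to use 1 of the highly effective contraception methods if they wish to continue their HRT"; otherwise they must stop HRT so that their status can be confirmed before enrolment.
- **Female subjects.** A table begins with "Highly Effective Contraceptive Methods That Are User Dependent" and continues with user-independent methods. Condoms are not in it.

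Protocol Section 15 gives the appendices the same standing as the body of the text: "All appendices attached hereto and referred to herein are made part of this clinical trial protocol".

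**The concern.** E05 is the numbered criterion that a site works through when it decides on entry, and Section 10.1.4 has the criteria rechecked at Cycle 1 Day 1. If E05 and Appendix C give different answers for the same patient, and neither says which prevails, enrolment depends on which page the site relies on.

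What is at stake is protection of a fetus from exposure to a conjugate whose payload, DM4, is described in Protocol Section 4.1 as an anti-mitotic agent. Male patients are foreseen: no criterion limits sex, Appendix C has a section for men, Section 10.4.1.3 makes pregnancy in a male patient's partner an adverse event of special interest, and SAP Section 2.1.1 tabulates gender as male or female. The trial's serum pregnancy tests cover female participants, so for the partner of a male patient the contraception rule is the main safeguard.

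**Working it through.** No arithmetic applies. The check sets E05 against Appendix C for each type of patient who proposes to rely on condoms only, in a country whose rules accept condoms.

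| Condom-only patient | E05 alone | Appendix C | Result |
|---|---|---|---|
| Man, partner of reproductive potential | Not excluded | Not eligible: neither abstinent nor using a second method | Different answers |
| Man, partner pregnant or breastfeeding | Not excluded | Accepted | Agree |
| Woman continuing HRT, menopausal status in doubt | Not excluded, if classed as of reproductive potential | Not accepted: must use a listed highly effective method | Different answers, by inference |
| Other woman of reproductive potential | Not excluded | Condoms not in the table, but no sentence makes the table a condition of entry | No binding conflict shown |

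**Row 1.** Appendix C uses eligibility wording and sets two joint conditions: no sperm donation, and one of two options (abstinence, or condom plus a method failing in fewer than 1% per year). A condom alone meets neither option. The result does not depend on how E05 is read. If its reference to patients of reproductive potential includes men, condoms are on its list. If it means women only, E05 says nothing about men. Either way it does not exclude this man.

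**Row 3.** The HRT sentence stands in Appendix C under the heading for patients without reproductive potential, in the postmenopausal item. E05 applies only to patients with reproductive potential. The link is the WOCBP definition in the same appendix: a woman counts as fertile from menarche until she becomes postmenopausal, unless permanently sterile. A woman whose menopausal status is unresolved has not been shown to be postmenopausal, so she falls under E05 by inference.

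**Method lists.** The Appendix C table for women has 3 combined hormonal routes + 2 progestogen-only routes + implant + IUD + hormone-releasing intrauterine system + tubal occlusion + vasectomized partner + abstinence = 3 + 2 + 6 = 11 methods. Of the 5 methods in E05, condoms are the only one with no counterpart by type. The match on the others is not complete: Appendix C accepts oral hormonal methods only where they inhibit ovulation, and its note b asks for two methods where the study drug may interact with hormonal contraception. These counts describe the texts, not patients.

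**The case against.** The best reply is that E05 does not stand alone. The same sentence defers to country rules, points to the consent form and cites Appendix C, which Section 15 makes binding. A site that follows the stricter text satisfies both, so nobody is forced to break one rule in order to obey the other. The consent text, where E05 says the definition is documented, was not available for this review and may already ask for more. All of that is right, and it limits the consequence. It does not remove the mismatch: a bracketed reference to Appendix C does not tell the site that the appendix overrides the list in front of it, and a country rule may be looser than Appendix C.

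Three stronger readings are tempting and are not supported:

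- **That E05 and Appendix C contradict each other for every woman of reproductive potential.** The table stands under contraceptive guidance, and no sentence requires each such woman to use a method from it.
- **That the HRT conflict is explicit.** It needs the inference from the WOCBP definition shown above.
- **That E05 contradicts the sperm-donation rule.** E05 defines a contraceptive method and is silent on sperm donation. That is an omission, which Appendix C fills.

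Other safeguards exist: pregnant women are excluded (E04), serum pregnancy tests are done within 7 days before the first dose and at end of treatment, with tests before each cycle where regulation requires them, and drug is stopped if a participant becomes pregnant. They protect female participants and do not answer the point about men.

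**Conclusion.** The point holds for men with partners of reproductive potential: E05 as written would not exclude a condom-only man whom Appendix C makes ineligible, and nothing in the protocol says which text controls. For women who continue HRT with doubtful menopausal status it holds by inference. For other women of reproductive potential it is not shown.

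A reader might infer that such patients will be enrolled. The documents do not show that, since a site may apply the stricter text and the consent form may state it. The conclusion assumes only that a country's rules accept condoms. How many of the approximately 63 planned patients would be affected is not given and is probably small. The ORR analysis, sample size and other analyses are untouched. The correction is worth making because the safeguard concerns fetal exposure to an anti-mitotic payload and the wording change costs almost nothing.

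**What to change.** In both places where E05 appears (synopsis and Section 7.2.1), keep the period of treatment plus 6 months and add:

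*Contraception must meet all applicable conditions of Appendix C as a minimum, plus any stricter country-specific requirement. A condom alone is not sufficient for a man with a partner of reproductive potential (except under the Appendix C rule for a pregnant or breastfeeding partner), or for a woman who continues HRT while her menopausal status is in doubt.*

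Leave the Appendix C conditions for men as they are, including no sperm donation and the choice of condom or abstinence when the partner is pregnant or breastfeeding. Align the consent form if it says less.

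Whether every other woman of reproductive potential must use a method from the Appendix C table is a design choice for the sponsor and not part of this correction. Saying so either way would spare sites the question.

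The cost is a short protocol edit and, if needed, matching consent text. A few condom-only patients would be excluded, all of them patients whom Appendix C already does not accept.

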7.2.2 Exclusion criteria related to the current knowledge of Sanofi compound

- E 14. Acquired immunodeficiency syndrome (AIDS-related illnesses) or known HIV disease requiring antiretroviral treatment.
- E 15. Known active hepatitis A, B, or C infection that requires treatment.
- E 16. Known intolerance to infused protein products including other monoclonal antibodies and ADCs.
- E 17. Poor bone marrow reserve as defined by absolute neutrophil count (ANC) $<1.5 \times 10^9/L$ or platelets $<100 \times 10^9/L$ or hemoglobin $<9 \text{ g/dL}$.
- E 18. Poor organ function as defined by 1 of the following:
 - a) Total bilirubin $>1.5 \times$ upper limit of normal (ULN) (except patients with Gilbert's syndrome: total bilirubin $\leq 3.0 \times$ ULN, with direct bilirubin $\leq 1.5 \times$ ULN),
 - b) Aspartate aminotransferase (AST), alanine aminotransferase (ALT), or alkaline phosphatase $>2.5 \times$ ULN; except $>5 \times$ ULN in case of documented liver metastasis or alkaline phosphatase $>5 \times$ ULN in case of documented bone metastasis,
 - c) Serum creatinine $>1.5 \times$ ULN, except if calculated creatinine clearance $\geq 60 \text{ mL/min}$ (as per Cockcroft-Gault formula; see [Appendix E](#)).
- E 19. Symptomatic peripheral neuropathy Grade ≥ 2 (NCI CTCAE v.4.03).
- E 20. Previous history of chronic corneal diseases (even if asymptomatic) or unresolved acute nonrecurrent corneal conditions.
- E 21. Patients wearing contact lenses who are not willing to stop wearing them for the duration of the study.
- E 22. Medical conditions requiring concomitant administration of strong CYP3A4 inhibitors, unless it can be discontinued at least 2 weeks before 1st administration of SAR566658 (see [Appendix F](#)).
- E 23. Contraindications to the use of ophthalmic vasoconstrictor and/or corticosteroid as per package insert of each drug, including the following: increased intraocular pressure, prior or current glaucoma, narrow-angle glaucoma, ongoing eye infection, uncontrolled hypertension, known/suspected allergy to constituents of the preparation (such as sodium bisulfite).

